12.8 Vital Signs

Vital signs (supine systolic and diastolic blood pressure, heart rate/pulse, body temperature) and changes from baseline at each time point will be presented by treatment group and cohort.

Listings for all vital signs will be presented.

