## Respiratory

Respiratory safety pharmacology studies of (2R,6R)-Hydroxynorketamine were performed in male RccHan® WIST rats. Single doses of 25, 175, and 300 mg/kg were administered, and each animal was subjected to head-out plethysmography for a duration inclusive of the infusion period through 5.5 hours postdose and 24 hours postdose. Transient changes in respiratory parameters were dose-related in magnitude and had resolved by 1.5 hours after the end of infusion. Respiration rate increases were noted for animals administered  $\geq$ 25 mg/kg, with compensatory tidal volume decreases observed for animals administered  $\geq$ 175 mg/kg. Given the compensatory differences in respiration rate and tidal volume, evident changes in minute volume were limited to a brief increase for animals administered 300 mg/kg.

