## Definitive GLP toxicity studies

Definitive toxicology studies of (2R,6R)-Hydroxynorketamine were performed in two species (rat and dog) and were supported by toxicokinetics. Male and female rats were administered 0, 25, 175, or 350 mg/kg/dose (2R,6R)-Hydroxynorketamine on Days 1, 4, 8, 11, 15, 18, 22, and 25. (2R,6R)-Hydroxynorketamine-related clinical observations for males included dose-dependent squinting eyes and low carriage and red discolored hair coat for males administered  $\geq$ 175 mg/kg/dose and ataxia, swollen nose, and sternal recumbent body position (one animal) for males administered 350 mg/kg/dose. (2R,6R)-Hydroxynorketamine-related clinical observations for females included

dose-dependent hypoactivity and ataxia for females administered ≥175 mg/kg/dose and squinting eyes for females administered 350 mg/kg/dose. Irregular/labored respiration was also noted for animals (male and female) administered  $\leq$ 350 mg/kg/dose and it was not clear whether this was related to (2R,6R)-Hydroxynorketamine dosing. All observations were transient, occurred close to tmax (1-minute postdose), generally resolved by 60 minutes postdose, and did not correlate with any changes in food consumption or body weight; therefore, they were considered nonadverse for animals administered 175 mg/kg/dose. However, these findings were considered adverse for animals administered 350 mg/kg/dose due to mortality, recumbence, and minimal decrease in male body weight/body weight gain (females experienced no change in body weight). Additionally, at the terminal sacrifice, (2R,6R)-Hydroxynorketamine-related increased liver weight parameters were noted in males administered 350 mg/kg/dose and correlated with the microscopic finding of minimal centrilobular hepatocyte hypertrophy. No (2R,6R)-Hydroxynorketamine-related microscopic findings or effects on organ weight parameters were observed at the recovery sacrifice, which was consistent with reversibility. Thus, the no observed adverse effect level (NOAEL) in rats was determined to be 175 mg/kg/dose. This dose level corresponded to mean maximum plasma concentration (Cmax) and AUC values of 150,000 ng/mL and 308,000 ng\*hr/mL, respectively, in males and 147,000 ng/mL and 315,000 ng\*hr/mL, respectively, in females on Day 25 of the dosing phase.

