
 
Activated partial thromboplastin time
 
Prothrombin time
 
International normalized ratio
 
	
 
Cannabinoids
 
Amphetamines
 
Barbiturates
 
Cocaine
 
Opiates
 
Benzodiazepines
 
Phencyclidine
 
Methadone
 
Cotinine
 
Alcohol (Breathalyzer)
 
	
 
Hepatitis B surface antigen
 
Hepatitis C antibody
 
Human immunodeficiency virus 1 & 2 antibodies
 

Table 8: Clinical laboratory evaluations

VS will be monitored according to the Time and Events Schedule for the SAD study (Table 1), MAD study (Table 2), and CSF Capture Study (Table 3) and will include blood pressure, pulse rate, respiration, and temperature. The PI or designee will verify the eligibility of each Subject with out-of-range VS and document approval prior to dosing.

Systemic blood pressure and pulse will be continuously monitored throughout drug administration and for 2 hours after the conclusion of study drug infusion. Monitoring of these parameters will be accomplished with a correct-sized finger cuff placed on either the index or middle finger and the Nexfin noninvasive continuous blood pressure monitor.

The ECG measurements, collected in triplicate, will be monitored using a 12-lead ECG signal according to the Time and Events Schedule for the SAD study (Table 1), MAD study (Table 2) and CSF Capture study (Table 3). During the collection of the baseline ECGs, Subjects should be in a quiet setting without distractions (eg, television or cell phones). Subjects should rest in a recumbent position for at least 5 minutes before ECG collection and should refrain from talking or moving arms or legs. Baseline ECG recordings should be taken at a time independent of blood sampling or VS measurements.

Subjects will be instructed to tell the study physician and/or research personnel of any AEs that occur at any time during the study. Subjects will be monitored for AEs from dose administration through the end-of-study.

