# **13.1 SAFETY DATA**

All investigational product and protocol procedure related AEs will be listed, and if the frequency of events allows, safety data will be summarized using descriptive methodology.

Each incidence of investigational product and protocol procedure related AEs will be presented by severity and by association with investigational product as perceived by the PI. Symptoms/AEs reported to occur prior to study entry will be distinguished from those reported as new or increased in severity during the study. All AEs and symptoms will be classified by the most suitable term using the MedDRA and summarized by SOC and preferred term, by severity, by relationship to study drug and study procedure, and by study drug dose.

The number of investigational product-related SAEs will be reported.

Safety parameters that will be assessed include clinical lab parameters, VS, and ECG parameters. The parameters will be listed and summarized using standard descriptive statistics. Additional analysis will be performed if warranted upon review of the data.

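### SAP 12.8 leaves respiration out of the vital-sign summaries, although the protocol collects it and says vital signs will be summarised

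*SAP*

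**What the plan says.** Protocol 12.8 defines the vital signs to be collected: they "will include blood pressure, pulse rate, respiration, and temperature". Protocol 13.1 names vital signs among the safety parameters and commits to a presentation: "The parameters will be listed and summarized using standard descriptive statistics".

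SAP 12.8 is narrower: "Vital signs (supine systolic and diastolic blood pressure, heart rate/pulse, body temperature) and changes from baseline at each time point will be presented". These displays are split by arm and dose cohort. The section then adds: "Listings for all vital signs will be presented". SAP 9.1 counts vital signs among the primary endpoints. SAP 7 sets the general display: each active cohort, overall active for SAD and MAD, and pooled placebo, within each substudy.

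On the nonclinical side, Protocol 2.3 (Respiratory) describes the rat study: "Single doses of 25, 175, and 300 mg/kg were administered, and each animal was subjected to head-out plethysmography". It reports: "Respiration rate increases were noted for animals administered" 25 mg/kg or more.

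**The concern.** Of the vital signs collected, one has no planned summary, and the SAP gives no reason for dropping it. It is also the vital sign with a specific nonclinical finding on its rate. Listings show individual readings subject by subject. A gradual trend across dose cohorts is easier to see in a dose-by-time table beside pooled placebo.

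At stake is whether the final report can describe respiration by dose from planned output. Without a planned table, the report either says nothing in summary form or relies on a table added after the SAP was fixed.

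**Working it through.** **1. Collected against summarised.**

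| Vital sign | Collected (Protocol 12.8) | Listed (SAP 12.8) | Summarised, with change from baseline (SAP 12.8) |
|---|---|---|---|
| Blood pressure | yes | yes | yes |
| Pulse | yes | yes | yes |
| Respiration | yes | yes | no |
| Temperature | yes | yes | yes |

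Three of four are summarised; the difference is exactly respiration. Protocol 13.1 calls for both listing and summary, so the SAP as written falls short of the protocol on this one item.

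**2. Is the SAP list closed?** It reads that way. SAP 12.8 does not mark its parenthesis as examples, whereas SAP 12.2 does so for baseline characteristics. Where the SAP wants listings only, it says so (as-needed urine microscopy, SAP 12.7). Where it wants no descriptive statistics, it says so (C-SSRS, SAP 12.12). It says neither about respiration, so an oversight is more likely than a choice.

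**3. The nonclinical finding, in full.** Doses tested were 25, 175 and 300 mg/kg and the rate rose at 25 mg/kg and above, so 3 of 3 doses were affected. The same section says the changes were transient, related to dose in size, and over by 1.5 hours after the infusion ended. Tidal volume fell in compensation at 175 mg/kg and above, and minute volume changed evidently only at 300 mg/kg, as a brief increase. The GLP rat study (Protocol 2.4) noted irregular or labored breathing but could not say whether the drug caused it. Protocol 2.7 concludes that no respiratory liability is predicted.

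**4. Dose scaling.** The plan's own figures reproduce: 175 / 6.2 = 28.2 mg/kg (Protocol 8.5), and 28.2 / 4.0 = 7.05, the stated margin of about 7. The same factor gives 25 / 6.2 = 4.03 mg/kg for the lowest rat dose with a raised rate, against a top SAD dose of 4.0 mg/kg.

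**5. What the schedule can show.** Each dosing day has six vital-sign readings: one an hour before infusion and five after its start (1, 2, 4, 8 and 12 hours). Suppose, as an assumption, that the human time course matched the rat's. An effect ending 1.5 hours after a 40-minute infusion would end at 40 + 90 = 130 minutes from the start. Only the nominal 60- and 120-minute readings fall inside that, so 2 of 5 post-dose points. With the ±30 minutes allowed by Protocol 12.8, the second could be taken as late as 150 minutes, which is outside the window. Continuous monitoring during and after the infusion covers blood pressure and pulse only.

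**6. Numbers per group.** The total is 48 + 16 + 6 = 70 or 48 + 16 + 8 = 72 subjects, because the Protocol synopsis gives 6 for the CSF cohort while Protocol 7.0 and 12.4 and SAP 10 give 8. Each SAD or MAD cohort has 6 active subjects; CSF has 4 or 5. Pooled placebo is 6 × 2 = 12 in SAD, 2 × 2 = 4 in MAD, and 2 or 3 in CSF.

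**7. Precision of one cohort mean.** The documents give no standard deviation for change in respiratory rate. Assuming 2 to 4 breaths/min and n = 6, the 95% half-width is 2.571 × SD / √6:

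- SD 2: 2.571 × 2 / 2.449 = 2.1 breaths/min
- SD 4: 2.571 × 4 / 2.449 = 4.2 breaths/min

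**The case against.** The strongest case for leaving the SAP alone is that nothing is lost. Every respiration reading will be listed. A change that the investigator judges clinically significant becomes an adverse event under SAP 12.6, and adverse events are summarised by dose. Protocol 10.3 bases escalation on review of all available safety data to Day 3 (SAD) or at least Day 12 (MAD), and its study halting rules name vital-sign events. SAP tables come only after the last visit and database lock (SAP 11.1), so they play no part in those decisions. The rat findings were brief and largely compensated. All of this stands, and it limits the point to reporting.

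One could also argue that SAP 12.5, which promises summaries for all safety analyses, already covers respiration. That is weak: the specific list in SAP 12.8 is what a programmer would follow.

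What the objection does not remove is the mismatch. The protocol promises a summary of vital signs, and the SAP supplies one for three of the four.

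**Conclusion.** The point holds as a minor inconsistency between Protocol 12.8 and 13.1 on one side and SAP 12.8 on the other. Its size is one of four collected vital signs without a descriptive summary. It rests on reading the SAP parenthesis as a complete list.

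Three stronger readings are tempting, and the documents do not support them:

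- *A respiratory safety signal would go unseen during the trial.* Escalation review, adverse-event capture and listings all remain in place.
- *A table would reveal a shift of a few breaths per minute in a cohort.* With six active subjects and the assumed standard deviations, a shift of that size is close to the uncertainty of one cohort mean, and perhaps two of the five post-dose points would be informative. The table's use is to display a trend across doses, not to detect an effect in one cohort.
- *The 4.03 mg/kg scaled figure shows no margin to the top SAD dose.* Protocol 2.3 gives neither plasma exposure nor infusion duration for that rat study, so scaling alone cannot show a comparable peak exposure. The scaled figure is context for why respiration is worth tabulating, and predicts nothing about humans.

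**What to change.** In SAP 12.8, add respiratory rate to the named vital signs. Summarise observed values and change from baseline at each scheduled time point, including the one pre-infusion and five post-dose readings on dosing days. Present them by active cohort and pooled placebo within SAD, MAD and CSF, using the display already set in SAP 7. Describe the table as a descriptive display of any trend across doses, with no test.

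The cost is two words in the SAP and one table block. The data are already collected. The change should be made before database lock and unblinding. If respiration was left out on purpose, the SAP should say so and give the reason, because Protocol 13.1 promises a summary.

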12.9 Physical Examinations

Descriptive statistics for weight and BMI at baseline and changes from baseline at each assessment time point will be presented by treatment group and cohort.

A listing of physical examination data for all subjects will be provided.

12.10 Ocular Examinations

Descriptive statistics for visual acuity and color vision at baseline and changes from baseline at each assessment time point will be presented by treatment group and cohort.

A listing of ocular examination data for all subjects will be provided.

12.11 Mood and Cognitive Assessment (POMS)

Descriptive statistics for total mood disturbance (TMD) at baseline and changes from baseline at each assessment time point will be presented by treatment group and cohort.

A listing of POMS data for all subjects will be provided.

12.12 Suicide Screen (C-SSRS)

Descriptive statistics for suicidal behavior or ideations will not be provided.

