6.5 On Treatment Population

All participants who completed all doses for their treatment group.

7. General Analysis Conventions

Analyses will be stratified by treatment assignment, dose groups, and sub studies (SAD, MAD, CSF):

- SAD
 - Cohorts 1 through 6 (2R,6R)-Hydroxynorketamine individually
 - Overall (2R,6R)-Hydroxynorketamine
 - Overall placebo
- MAD
 - Cohorts 1 through 2 (2R,6R)-Hydroxynorketamine individually
 - Overall (2R,6R)-Hydroxynorketamine
 - Overall placebo
- CSF
 - Cohort 1 (2R,6R)-Hydroxynorketamine individually
 - o Overall placebo

General statistical approaches are presented below.

All subjects in the Safety Population will be included in the safety analysis grouped by study, cohort, and treatment group. Statistical analysis of safety data will be descriptive.

Baseline is defined as the last non-missing assessment prior to dosing of study medication.

For continuous variables, summaries will include sample size, mean, median, 25th and 75th percentiles, standard deviation, minimum, and maximum. For categorical variables, the summaries will include frequencies and corresponding percentages. No inferential hypothesis testing will be performed. Repeat or unscheduled results will not be included in the summaries, but will be listed. Data from placebo subjects will be pooled for final presentations.

Missing data results will not be imputed. Data summaries and analyses (e.g. means) will be calculated using all available data. If the start day for an AE is missing, day of study drug administration will be used and AE will be considered treatment emergent. Neither month nor year will be imputed for AE.

Planned analyses are descriptive or exploratory. If presented, significance level and confidence intervals will use alpha of 0.05. No adjustments for multiple testing are planned.

Analyses will be performed using a UNIX server based installation of SAS Software, version 9.4 or newer.

8. Outcomes

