8.1 Primary Outcome Measures

Study outcomes include

- Completion of all dosing levels and timepoints with full collection of all safety data
- Adverse event (AE) tabulation
- Clinical laboratory tests

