9.1 Primary Endpoints

The primary endpoints are the following:

- 1) Study Drug Exposure
- 2) Concomitant Medications
- 3) Safety Analysis
- 4) Adverse Events
- 5) Clinical Laboratory Results
- 6) Vital Signs
- 7) Physical Examinations
- 8) Ocular Examinations
- 9) Mood and Cognitive Assessment (POMS)
- 10) Suicide Screen (C-SSRS)
- 11) Clinician Administered Dissociative States Scale
- 12) Modified Observer's Assessment of Alertness/Sedation Scale (MOASS)

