12.5 Safety Analyses

The Safety Population will be used for all safety analyses unless otherwise indicated. All analyses will include summaries by treatment group and study cohort. All summaries will be supported by data listings.

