12.7 Clinical Laboratory Results

Summary statistics of observed and change from baseline data will be presented for each treatment group, cohort, and dose where applicable. Shift tables summarizing the numbers of subjects shifting from normal pre-dose values to abnormal post-dose values will also be presented where applicable.

Lab tests included will be all in the hematology and coagulation panel, biochemistry panel, and urinalysis panel (as needed lab tests: RBC, WBC, hyaline casts, cellular casts, and granular casts will only be presented as listings).

Listings for all safety laboratory evaluations will also be presented.

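### The SAP names the C-SSRS as a primary endpoint but plans neither a summary nor a listing of it, so about 288 assessments scheduled after the first dose have no planned output.

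*SAP*

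**What the plan says.** SAP 9.1 lists the C-SSRS as a primary endpoint ("10) Suicide Screen (C-SSRS"). SAP 8.1 does not name it, but its first outcome is "Completion of all dosing levels and timepoints with full collection of all safety data", and the Safety part of the protocol synopsis counts the C-SSRS among the safety assessments.

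The whole of SAP 12.12 is: "Descriptive statistics for suicidal behavior or ideations will not be provided".

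The neighbouring sections read differently. SAP 12.7 says "Listings for all safety laboratory evaluations will also be presented", SAP 12.8 says "Listings for all vital signs will be presented" and SAP 12.11 says "A listing of POMS data for all subjects will be provided". SAP 12.9, 12.10, 12.13 and 12.14 also each name a listing.

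Two general SAP rules concern listings. SAP 12.5 says "All summaries will be supported by data listings". SAP section 7 (General Analysis Conventions) says "Repeat or unscheduled results will not be included in the summaries, but will be listed".

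Protocol 13.1 promises listings and summaries of laboratory, vital-sign and ECG parameters. It allows further analysis where a review of the data calls for it. It does not mention the C-SSRS.

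**The concern.** Protocol 8.7 includes the scale because of the planned indication and the drug's relationship to ketamine. The schedules ask for it repeatedly after dosing. A reader of the final report would expect to learn, for each dose, how many subjects were assessed and how many had a positive item that was not there before dosing. In healthy volunteers the likely answer is none. That answer carries weight only if the report shows that the question was asked and answered.

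If SAP 12.12 is followed as written, no table or listing does this. An adverse-event table does not fill the gap. It shows neither the denominator nor the items that were positive, and it cannot separate subjects who were asked and answered no from subjects who were not asked. SAP 8.1 makes full collection of safety data an outcome, and no planned output would show it for this scale.

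**Working it through.** **1. Does any other text supply an output?**

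- SAP 12.5 attaches listings to summaries. SAP 12.12 removes the C-SSRS summary, so the rule has nothing to attach to. SAP 12.5 also says that analyses will include summaries by treatment group and cohort. A generous reader could take that to imply C-SSRS output, but the general rule would then contradict the specific one.
- SAP section 7 promises listings only for repeat or unscheduled results. Scheduled C-SSRS assessments are neither.
- Protocol 13.1 names laboratory, vital-sign and ECG parameters. Anything further is conditional.
- The other two analysis plans named in protocol 12.1 cover PK and qEEG, so the safety SAP is where the C-SSRS belongs.

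None of the four supplies a planned output. Of the eight sections SAP 12.7 to 12.14, seven name a listing, and 12.12 is the one that does not.

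**2. How many assessments are involved?**

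The planned numbers in SAP section 10 reproduce as cohorts × (active + placebo):

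- SAD: 6 × (6 + 2) = 48
- MAD: 2 × (6 + 2) = 16
- CSF: 1 × (5 + 3) = 8
- Total: 72

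The C-SSRS visits marked from Day 1 onward in SAP 3.1 to 3.3 (protocol Tables 1 to 3) are:

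- SAD: Days 1 and 2, so 2
- MAD: Days 1, 2, 4, 5, 7, 8, 9, 11, 12, 15 and 17-19, so 11
- CSF: Days 1 and 2, so 2

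The legends of the protocol's timeline figures place the Day 1 and Day 2 assessments within about 4 and 24 hours after the infusion starts. Day 1 therefore counts as post-dose.

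Assessments after the first dose = subjects × visits:

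- SAD 48 × 2 = 96; MAD 16 × 11 = 176; CSF 8 × 2 = 16; total 288
- Active: 36 × 2 + 12 × 11 + 5 × 2 = 214, in 53 subjects
- Placebo: 12 × 2 + 4 × 11 + 3 × 2 = 74, in 19 subjects

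**3. Sensitivity to two readings.**

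- CSF cohort of 6 (protocol synopsis) instead of 8 (protocol 7.0 and 12.4, SAP 5.3 and section 10): 96 + 176 + 6 × 2 = 284.
- MAD Day 7 left out, because it falls the day before dose 3: 288 − 16 = 272.

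**The case against.** The strongest reply has five parts.

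*Not tabulating is defensible.* Subjects are healthy, and protocol 9.3 excludes anyone with a history of mental illness or of suicidal or homicidal ideation. There are at most 6 active subjects per dose, and positives should be very rare. This is a fair reason to leave out means and percentages. It is no reason to leave out a listing, and rarity makes a simple count easier to produce and read.

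*Other routes exist.* The adverse-event definitions in protocol 12.9 and SAP 12.6 are broad, so new ideation may well be recorded as an event. Protocol 13.1 leaves room for extra analysis, and SAP 12.12 does not forbid a listing or a narrative. This stands. The documents do not support the inference that the report cannot describe suicidality. They support the narrower statement that no planned output would show C-SSRS results.

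*Stopping is untouched.* The protocol synopsis and protocol 8.7 make acute suicidality on the C-SSRS a ground for stopping escalation or dosing, so a reader might infer that SAP 12.12 weakens subject protection. It does not. Those decisions are made during the trial by the investigator, the medical monitor and the sponsor. SAP 11.1 places the planned analyses after the last subject's last visit. Protocol 10.3 requires the reasoning behind any halt to be documented and sent to the IRB.

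*The SAP is uneven elsewhere.* SAP 12.6 on adverse events holds only definitions, and ECG has no section at all. The list in SAP 9.1 also includes concomitant medications, so the primary label carries little weight. Both remarks are fair, and they make seven of eight weaker evidence about intent. But SAP 12.12 is not merely silent: it rules the summary out.

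*The count is not a measure of harm.* Correct. It counts scheduled forms, not missed signals.

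**Conclusion.** The point holds. As written, the SAP leaves a collected safety scale that it calls a primary endpoint without a planned summary or listing. About 288 assessments scheduled after the first dose in 72 subjects are affected, with 284 or 272 under the two other readings. The figures assume full planned enrolment and no missed visits, and take post-dose to mean after the first dose.

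The consequence is limited to reporting: no planned output would give C-SSRS positives by dose, or a documented zero with the number assessed. It is worth correcting, but it does not threaten the conduct of the trial.

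A reader might also infer that the post-dose responses would be hard to interpret, because Appendix 3 reproduces only the Baseline/Screening form. The documents do not support this. They do not say which form is used after dosing, the look-back period on the reproduced form is blank, and protocol 12.1 supplies the questionnaires as separate study materials.

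**What to change.** Replace the sentence in SAP 12.12 with two outputs for the Safety Population:

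1. A by-subject, by-visit listing of all C-SSRS responses, including screening and Day -1.
2. A count of subjects with any new post-dose positive ideation or behavior item, shown with the number assessed, for each dose and pooled placebo within SAD, MAD and CSF. An item is new if it was not positive before the first dose.

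No percentages, means or tests are needed. The cost is one listing and one small table. All the data are already scheduled for collection, and the grouping is the one in SAP section 7. The change should be made before the SAP is approved for database lock.
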